8.2.3. Safety Monitoring

The Lilly CRP will monitor safety data throughout the course of the study.

Lilly will review SAEs within time frames mandated by company procedures. The Lilly CRP will, as is appropriate, consult with the functionally independent Global Patient Safety therapeutic area physician or clinical scientist, and review:

- trends in safety data
- laboratory analytes ([Attachment 3](#))
- adverse events, including ramucirumab AESI and pembrolizumab ECI (Section [8.2.1.1](#)).
- Details for hepatic monitoring depend upon the severity and persistence of observed laboratory test abnormalities. To ensure patient safety and comply with regulatory guidance, the investigator may consult with the Lilly CRP regarding collection of specific recommended clinical information and follow-up laboratory tests. See Site Guidance Document for Drug-Induced Liver Injury.

8.3. Pharmacokinetics

Pharmacokinetic samples to determine ramucirumab PK will be collected as specified in [Attachment 2](#).

Blood samples will be drawn for all patients for the assessment of ramucirumab concentrations in serum (also known as bioanalytical samples). Sampling times were selected to coincide with expected C_{max} and C_{min} and with consideration to draw minimum volume of blood from patients and ensuring that the patients do not need to make an extra visit to provide these samples.

Instructions for the collection and handling of bioanalytical blood samples will be provided by the Sponsor. The actual start and end date and time of ramucirumab infusion administration must be recorded on the eCRF. The actual date and time that each bioanalytical blood sample was drawn must be recorded on the laboratory accession page after the sample is drawn.

Ramucirumab concentrations in bioanalytical serum samples will be measured using a validated assay methodology in a laboratory designated by the Sponsor.

Bioanalytical samples collected to measure ramucirumab concentration will be retained for a maximum of 1 year following last patient visit for the study.

8.4. Biomarkers

Where local regulations and ethical review boards (ERBs) allow, these samples will be collected for biomarker research as discussed below and specified in the Sampling Schedule ([Attachment 2](#)).

All biomarker samples will be coded with the patient number. These samples and any data generated can be linked back to the patient only by the investigator site personnel. Samples will be destroyed according to a process consistent with local regulations.

It is possible that biomarker data for patients in the study has already been generated from samples that were collected and analyzed prior to enrolling in this trial. This may include data

generated from genetic analyses. If available, these data may be requested from medical records for use in the research described in Section 8.4.2.

8.4.1. Genetics

Whole Blood Sample for DNA Collection:

A whole blood sample will be collected for pharmacogenetic analysis where local regulations and ERBs allow. These samples **are not** being collected to create a biobank for conducting unspecified disease or population genetic research either now or in the future.

Samples may be used to investigate variable response to study treatment and to investigate genetic variants thought to play a role in cancer. Assessment of variable response may include evaluation of AEs or differences in efficacy. These studies may include but are not limited to the VEGF pathway and immunomodulatory mechanisms to evaluate their association with observed response to study treatment.

Samples will be retained for a maximum of 15 years after the last patient visit, or as local regulations and ERBs allow, for the study at a facility selected by the Sponsor. This retention period enables use of new technologies, response to regulatory questions, and investigation of variable response that may not be observed until later in drug development or when the drug is commercially available.

Molecular technologies are expected to improve during the 15-year storage period and therefore cannot be specifically named. However, existing approaches include whole genome or exome sequencing, genome-wide association studies, candidate gene studies, and epigenetic analyses. Regardless of the technology utilized, genotyping data generated will be used only for the specific research scope described in this section.

8.4.2. Tailoring and Pharmacodynamic Biomarkers

Samples will be collected for potential non-pharmacogenetic biomarker research. Samples will be collected at the times specified in the Schedule of Activities.

Samples may be used for research on the drug targets (PD-1 and VEGF Receptor 2), disease process, pathways associated with cancer, mechanism of action of ramucirumab and/or pembrolizumab, and/or research method or in validating diagnostic tools or assay(s) related to cancer.

Samples will be retained for a maximum of 15 years after the last patient visit, or as local regulations and ERBs allow, for the study at a facility selected by the Sponsor. This retention period enables use of new technologies, response to regulatory questions, and investigation of variable response that may not be observed until later in drug development or when the drug is commercially available.

Required samples for biomarker research to be collected from all patients in this study as specified in the study schedule are the following:

- EDTA plasma

- peripheral mononuclear blood cells from whole blood
- tumor tissue at baseline (see Inclusion Criterion [4] and the paragraph below).

For the submission of baseline tumor tissue sample, formalin-fixed paraffin-embedded tumor tissue sample blocks are preferred. If submitting unstained cut slides, freshly cut slides should be submitted to the testing laboratory within 7 days from when the slides are cut. In addition, all archival samples should be discussed with the Sponsor before submission. A formalin-fixed paraffin-embedded tumor tissue block obtained within 3 months prior to enrollment and following most recent systemic treatment will be considered by the Sponsor.

Optional samples for biomarker research that should be collected from patients in the study where possible are the following:

- tumor tissue/biopsy that becomes available during the study treatment period

8.5. Samples for Immunogenicity Research

Blood samples for immunogenicity testing will be collected to determine anti-drug antibody (ADA) production against ramucirumab. The specific time points are listed in [Attachment 2](#). Sample collection, storage, and shipment instructions for blood samples will also be provided in the Procedures Manual.

Pretreatment and post-treatment samples will be collected and assayed for the presence of ADA using an immunoassay. The number and percentage of patients with positive antidirug response will be summarized. In the event of an IP- related infusion reaction, every effort should be made to collect a blood sample for anti-ramucirumab antibody determination, as well as a blood sample for ramucirumab serum concentration, as close to the onset of the reaction as possible, at the resolution of the event, and 30 days following the event.

Samples may be stored for a maximum of 15 years following last patient visit for the trial at a facility selected by the Sponsor to enable further analysis of immune responses to ramucirumab. The duration allows the Sponsor to respond to regulatory requests related to ramucirumab.

8.6. Health Economic and Outcomes Research

This section is not applicable to this protocol.

9. Statistical Considerations and Data Analysis

9.1. Determination of Sample Size

The primary objective for the DLT Phase 1a and Expansion Phase 1b is to evaluate safety and tolerability. The sample size of Expansion Phase 1b was selected to allow adequate assessment of safety at the recommended doses for ramucirumab and pembrolizumab for each tumor type and dose schedule, separately.

The following sample sizes apply to each phase of the study:

Phase 1a Dose-Limiting Toxicity Observation: up to 12 DLT-evaluable patients

Phase 1b Expansion: 155 patients;

- 15 patients each for Gastric-GEJ (2nd - 3rd Line) Cohorts A and B (2nd - 3rd Line)
- 25 patients each for:
 - BTC (2nd - 3rd Line) Cohort A1
 - Gastric-GEJ (1st Line) Cohort A2
 - NSCLC (2nd - 4th Line) Cohort C
 - Urothelial (2nd - 4th Line) Cohort D
 - NSCLC (1st Line) Cohort E

The primary objective of Study JVDF is the safety and tolerability of ramucirumab in combination with pembrolizumab. During Expansion Phase 1b, 25 to 30 patients per tumor type will be treated, to provide a preliminary assessment of tumor response and an assessment of safety. For each of the tumor types, the ORR values in the simulations are provided as a reference for estimation of statistical power rather than a basis of any decision criteria. All efficacy endpoints will be utilized to determine next steps of development of the combination.

For Gastric-GEJ and BTC (2nd -3rd line), and NSCLC and Urothelial (2nd to 4th line), the null hypothesis is based on the assumption that the ORR is no greater than 10% to 15% and the target treatment effect (alternative response rate) of the combination treatment on ORR is greater than 20% to 30%. Based on these assumptions, a sample size of n=25 to 30 (n=30 for combined Gastric Cohorts A and B) provides statistical power of approximately 60% to 90%, with a 1-sided 0.20 significance level ([Table JVDF.8](#)).

Table JVDF.8. Summary of Statistical Power for Overall Response Rates for NSCLC 2-4L, Bladder 2-4L, BTC 2-3L, and Gastric 2-3L

	NSCLC, Bladder, and BTC				Gastric (combined preliminary efficacy)			
	Low Case	High Case	Low Case	High Case	Low Case	High Case	Low Case	High Case
	N=25	N=25	N=25	N=25	N=30	N=30	N=30	N=30
Null response rate	10%	10%	15%	15%	10%	10%	15%	15%
Alternative response rate	20%	25%	25%	30%	20%	25%	25%	30%
Power	57.9%	78.6%	62.2%	80.7%	74.5%	90.2%	65.2%	84.0%

Abbreviations: BTC = biliary tract cancer; L = line; N = number of patients; NSCLC = non-small cell lung cancer.

Note: Low case = 10% difference between alternative response rate and null response rate for overall response rate; High case = 15% difference between alternative response rate and null response rate for overall response rate.

For the first-line NSCLC and Gastric-GEJ, the null hypothesis is based on the assumption that the ORR is no greater than 30% to 35% and the target treatment effect (alternative response rate) of the combination treatment on ORR is greater than 45% to 55%. Based on these assumptions, a sample size of n=25 provides statistical power of approximately 65% to 90%, with a 1-sided 0.20 significance level (Table JVDF.9).

Table JVDF.9. Summary of Statistical Power for Overall Response Rates for NSCLC 1L and Gastric 1L

	NSCLC (1L) and Gastric (1L; combined preliminary efficacy)			
	Low Case	High Case	Low Case	High Case
	N=25	N=25	N=25	N=25
Null response rate	30%	30%	35%	35%
Alternative response rate	45%	50%	50%	55%
Power	75.8%	88.5%	65.5%	81.7%

Abbreviations: 1L = First-Line; N = number of patients; NSCLC = non-small cell lung cancer.

Note: Low case = 15% difference between alternative response rate and null response rate for overall response rate; High case = 20% difference between alternative response rate and null response rate for overall response rate.

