Most common AEs >20% in patients treated with MPDL3280A and bevacizumab were fatigue, diarrhea, nausea, pyrexia, vomiting, headache, and cough. Hodi et al. also demonstrated combining bevacizumab and ipilimumab (cytotoxic T-lymphocyte-associated antigen-4 [CTLA-4] blocker) can be safely administered in melanoma patients. The study findings provided a basis for further investigating future combinations of antiangiogenesis agents and immune checkpoint blockade (Hodi et al. 2014).

The manageable safety profile, clinical efficacy of these 2 agents individually, and the synergistic preclinical antitumor activity demonstrated, provide evidence supporting the rationale for clinically testing whether the simultaneous blockade of PD-1 and VEGF Receptor 2 enhances single-agent activity while maintaining an acceptable safety profile.

Table JVDF.1. Ramucirumab and Pembrolizumab Data Summary: Gastric-GEJ, NSCLC, and Urothelial Indications^a

Indication	Study Treatment	N	Efficacy	Safety	Reference
Gastric-GEJ	Ram	238	ORR: 3% Median PFS: 2.1 months Median OS: 5.2 months	Adverse reactions occurring at a rate of $\geq 10\%$ and in $\geq 2\%$ more in ramucirumab than in placebo group: hypertension (16% [all grades]; 8% [Grade 3-4]) and diarrhea (14% [all grades]; 1% [Grade 3-4])	Cyramza US Package Insert, April 2015
	Ram + Paclitaxel	330	ORR: 28% Median PFS: 4.4 months Median OS: 9.6 months	Adverse reactions occurring at a rate of $\geq 30\%$ and in $\geq 2\%$ more in ramucirumab + paclitaxel than in the paclitaxel control group: fatigue/asthenia (57% [all grades]; 12% [Grade ≥ 3]), neutropenia (54% [all grades]; 41% [Grade ≥ 3]), diarrhea (32% [all grades]; 4% [Grade ≥ 3]), and epistaxis (31% [all grades]), 0% [Grade ≥ 3]).	Cyramza US Package Insert, April 2015
	Pembro	39, PD-L1+ only	ORR: 22% 6-mo PFS rate: 24% 6-mo OS rate: 69%	Grade 3-5 drug-related AEs occurred in 4 patients, peripheral sensory neuropathy, fatigue, decreased appetite, hypoxia, and pneumonitis (n=1 each).	Muro et al. 2015 (ASCO GI Symposium)
NSCLC	Ram+ Docetaxel	628	ORR: 22.9% Median PFS: 4.5 months Median OS: 10.5 months	Adverse reactions occurred at a rate $\geq 30\%$ and $\geq 2\%$ more in the ramucirumab + docetaxel than in the docetaxel control group: fatigue/asthenia (55% [all grades]; 14% [Grade 3-4]), neutropenia (55% [all grades]; 49% [Grade 3-4]), and stomatitis/mucosal inflammation (37% [all grades]), 7% [Grade 3-4]).	Cyramza US Package Insert, April 2015

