	Pembro	495	ORR: 19.4% overall; 18% previously treated, 24.8% treatment naïve, 45.2% in PD-L1 strong + ($\geq 50\%$), 16.5% in PD-L1+ (1-49%), 10.7% in PD-L1- (<1%)	Most common AEs were fatigue, pruritus, and decreased appetite. Grade 3-5 drug-related AE occurred in 47 patients (9.5%), most commonly dyspnea (n=19, 3.8%) and pneumonitis (n=9, 1.8%).	Garon et al. 2015

Ramucirumab and Pembrolizumab Data Summary: Gastric-GEJ, NSCLC, and Urothelial Indications (concluded)

Indication	Study Treatment	N	Efficacy	Safety	Reference
Urothelial	Ram+ Docetaxel	46	ORR: 19.6%, median PFS: 5.1 months DCR: 67.4%	Most common AEs were fatigue (80.4%), decreased appetite (54.3%), nausea (54.3%), and neuropathy (50.0%). Grade ≥ 3 AEs, febrile neutropenia (19.6%), pneumonia (13%), and hypertension (4.3%) were higher with Doc + Ram.	Petrylak et al. 2015 (ASCO GU Symposium)
	Pembro	33, PD-L1+ only	ORR: 24% Median PFS: 8.6 weeks Median OS: 9.3 months (6-month OS rate: 58%)	Most common AEs were fatigue (n=6), peripheral edema (n=4), and nausea (n=3); Grade 3-4 drug-related AEs were reported for 4 patients (12%), with only rash seen in >1 patient (n=2).	O'Donnell et al. 2015 (ASCO GU Symposium)

Abbreviations: AE = adverse event; ASCO = American Society of Clinical Oncology; DCR = disease control rate; Doc = docetaxel; GEJ = gastroesophageal; GI = gastrointestinal; GU = genitourinary; N = number of patients; NSCLC = non-small cell lung cancer; ORR = objective response rate; OS = overall survival; PD-L1 = programmed death ligand 1; Pembro = pembrolizumab; PFS = progression-free survival; Ram = ramucirumab; US = United States.

^a Preliminary efficacy and safety data for BTC (2nd -3rd Line), NSCLC (1st Line) and Gastric/GEJ (1st Line) are described below this table.

Rationale for Expanding to Biliary Tract Cancer, First Line Gastric-GEJ, and First Line NSCLC***1). Biliary Tract Cancer:***

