5.1.2. Phase 1b

Phase 1b Expansion: 155 patients; 15 patients each for Cohorts A and B (2L-3L gastric-GEJ), 25 patients each for Cohorts A1, A2, C, D, and E (2L-3L BTC, 1L gastric-GEJ, 2L-4L NSCLC, 2L-4L urothelial cancer, and 1L NSCLC, respectively).

The primary objective of Study I4T-MC-JVDF (JVDF) is the safety and tolerability of ramucirumab in combination with pembrolizumab. During Expansion Phase 1b, 25 to 30 patients per tumor type will be treated, to provide a preliminary assessment of tumor response and an assessment of safety. For each of the tumor types, the objective response rate (ORR) values in the simulations are provided as a reference for estimation of statistical power rather than a basis of any decision criteria. All efficacy endpoints will be utilized to determine next steps of development of the combination.

For gastric-GEJ and BTC (2L-3L), and NSCLC and urothelial cancer (2L-4L), the null hypothesis is based on the assumption that the ORR is no greater than 10% to 15% and the target treatment effect (alternative response rate) of the combination treatment on ORR is greater than 20% to 30%. Based on these assumptions, a sample size of n=25 to 30 (n=30 for combined Gastric Cohorts A and B) provides statistical power of approximately 60% to 90%, with a 1-sided nominal 0.20 significance level ([Table JVDF.1](#)).

For first-line NSCLC and gastric-GEJ, the null hypothesis is based on the assumption that the ORR is no greater than 30% to 35% and the target treatment effect (alternative response rate) of the combination treatment on ORR is greater than 45% to 55%. Based on these assumptions, a sample size of n=25 provides statistical power of approximately 65% to 90%, with a 1-sided 0.20 significance level ([Table JVDF.2](#)).

Table JVDF.1. Summary of Statistical Power for Overall Response Rates for NSCLC 2-4L, Bladder 2-4L, BTC 2-3L, and Gastric 2-3L

	NSCLC, Bladder, and BTC				Gastric (combined preliminary efficacy)			
	Low Case	High Case	Low Case	High Case	Low Case	High Case	Low Case	High Case
	N=25	N=25	N=25	N=25	N=30	N=30	N=30	N=30
Null response rate	0.10	0.10	0.15	0.15	0.10	0.10	0.15	0.15
Target response rate	0.20	0.25	0.25	0.30	0.20	0.25	0.25	0.30
Power	57.9%	78.6%	62.2%	80.7%	74.5%	90.2%	65.2%	84%

Abbreviations: BTC = biliary tract cancer; L=line; N = number of patients; NSCLC = non-small cell lung cancer.

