5.3.10. Efficacy Analyses

For patients with PD, the initial determination of progression and the progression by irRECIST will be listed.

This Phase 1a trial was not designed to assess efficacy; however, antitumor activity is a secondary objective, and as such best overall response will be summarized for all patients evaluable for efficacy whose disease is assessable by RECIST v.1.1.

If appropriate, the following analyses will be performed for 2L-3L Gastric (Schedule1), 2L-3L Gastric (Schedule2), 1L Gastric, NSCLC (1L; 2L-4L), Urothelial (2L-4L), BTC (2L-3L), and 2L-3L Gastric (total).

- Objective response rate for each cohort will be estimated by dividing the total number of responders (RECIST v.1.1, irRECIST) by the number of patients whose disease at baseline is assessable by RECIST v.1.1. The estimates will be reported with exact 90% confidence intervals (CIs) for each treatment arm.
- Disease control rate for each treatment arm will be summarized and exact 90% CIs for each treatment arm will be provided.
- Progression-free survival will be estimated using a Kaplan-Meier (KM) method (Kaplan and Meier 1958) by median and exact 90% CI. Additional exploratory analyses using proportional hazards models to control for other factors may be performed. The PFS rate at 12, 18, and 24 weeks (including the 90% CI) may also be calculated. Efficacy analyses will be based on the enrolled patients.
- Overall survival, including 1- and 2- year survival rates, is determined from the date of first study treatment until death due to any cause. If the patient was alive at the data inclusion cut-off date for the analysis (or was lost to follow-up), OS will be censored on the last date the patient was known to be alive. The KM curves will also be presented.
- Individual changes in the tumor burden (sum of measurable lesions) over time will be presented graphically within a tumor type (waterfall plots and spider plots may be used) by tumor programmed death-1 T-cell co-receptor PD-1 expression at baseline.
- Duration of responses may be presented graphically using swimmer plots.
- Overall response rate will be summarized by tumor PD-1 expression at baseline.

In addition, exploratory analysis of TTR, DoR, and PFS may be conducted using irRECIST, and subgroup analysis of interest will be further explored.

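### Does the stated 58–90% ORR power mislead because the SAP reports a 90% interval, and because Cohort C's null lies below pembrolizumab alone?

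*Protocol*

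**What the plan says.** Protocol 9.1 and SAP 5.1.2 open by giving safety and tolerability as the primary objective and the basis for the size of the expansion. They then add an ORR reference.

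- **Previously treated cohorts:** "the null hypothesis is based on the assumption that the ORR is no greater than 10% to 15" per cent, and the target effect of "the combination treatment on ORR is greater than 20% to 30" per cent. The size is "a sample size of n=25 to 30 (n=30 for combined Gastric Cohorts A and B"), and this "provides statistical power of approximately 60% to 90%, with a 1-sided 0.20 significance level".
- **First-line cohorts:** nulls of 30% and 35%, alternatives of 45% to 55%, n=25, the same level, and power of about 65% to 90%.
- **Level in the SAP:** for the previously treated cohorts it is given as "with a 1-sided nominal 0.20 significance level".
- **Status of the figures:** the same sections say that the ORR values are there to indicate power and are not decision criteria, and that next steps will draw on all efficacy endpoints.
- **Analysis:** SAP 5.3.10 says of ORR that "The estimates will be reported with exact 90% confidence intervals (CIs) for each treatment arm". Protocol 9.4 also plans an estimate with an interval. Neither names a test, a null or a success threshold.
- **Background rate:** Table JVDF.1 gives, for pembrolizumab in non-small cell lung cancer, "ORR: 19.4% overall; 18% previously treated". The Introduction says the trial will test "whether the simultaneous blockade of PD-1 and VEGF Receptor 2 enhances single-agent activity".

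**The concern.** An exact two-sided 90% interval has a lower limit at the one-sided 0.05 level, whereas the power figures use one-sided 0.20. A cohort that just reaches the planning cut-off, 5 of 25 against a null of 10%, would be reported as 20% with a 90% interval of 8.2% to 37.5%, which still contains the null. A reader could take the power tables to mean that an active cohort will stand clear of its null with probability 58% to 90%, when the interval in the report would do so much less often.

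Cohort C adds a second worry. If the question is whether the combination improves on a single agent, a null of 10% or 15% looks too easy when pembrolizumab alone is listed at 18% in previously treated patients. A combination no better than pembrolizumab could exceed such a null without ramucirumab adding anything. At stake would be an over-optimistic reading of activity, and development steps taken on that reading.

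**Working it through.** **Inputs.** n, null p0 and alternative p1 come from protocol Tables JVDF.8 and JVDF.9 (SAP Tables JVDF.1 and JVDF.2). The level of 0.20 comes from protocol 9.1 and SAP 5.1.2. The 90% interval comes from SAP 5.3.10. The 18% comes from protocol Table JVDF.1.

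**Step 1: reproduce the stated power.** Take the smallest r with P(X ≥ r | n, p0) ≤ 0.20. Power is then P(X ≥ r | n, p1), with X binomial. For n=25 and p0=10%, P(X ≥ 4) = 0.236 and P(X ≥ 5) = 0.098, so r=5. At p1=20%, P(X ≥ 5) = 0.579, which is the tabulated 57.9%.

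**Step 2: impose a rule that the 90% lower limit exceeds p0.** This is the same calculation at 0.05. Finding the cut-offs directly from the Clopper-Pearson limit gives identical values.

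| n | p0 | p1 | r at 0.20 (actual size) | Power at 0.20 = tabulated | r for 90% limit > p0 | Probability |
|---|---|---|---|---|---|---|
| 25 | 10% | 20% | 5 (0.098) | 57.9% | 6 | 38.3% |
| 25 | 10% | 25% | 5 | 78.6% | 6 | 62.2% |
| 25 | 15% | 25% | 6 (0.162) | 62.2% | 8 | 27.4% |
| 25 | 15% | 30% | 6 | 80.7% | 8 | 48.8% |
| 30 | 10% | 20% | 5 (0.176) | 74.5% | 7 | 39.3% |
| 30 | 10% | 25% | 5 | 90.2% | 7 | 65.2% |
| 30 | 15% | 25% | 7 (0.153) | 65.2% | 9 | 32.6% |
| 30 | 15% | 30% | 7 | 84.0% | 9 | 56.9% |
| 25 | 30% | 45% | 10 (0.189) | 75.8% | 12 | 45.7% |
| 25 | 30% | 50% | 10 | 88.5% | 12 | 65.5% |
| 25 | 35% | 50% | 12 (0.125) | 65.5% | 14 | 34.5% |
| 25 | 35% | 55% | 12 | 81.7% | 14 | 54.3% |

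All 12 stated powers reproduce. The last column is also correct arithmetic, but it answers a question the plan does not ask: no section of either document compares the lower limit with 10%, 15%, 30% or 35%.

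**Step 3: Cohort C at a true ORR of 18%, n=25.**

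| Rule | Null 10% | Null 15% |
|---|---|---|
| Planning cut-off at 0.20 | ≥5: 47.7% | ≥6: 28.8% |
| 90% lower limit above null | ≥6: 28.8% | ≥8: 6.6% |

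The size of this worry depends on which rule is assumed. One cannot hold that the 0.20 test is never performed and also measure the harm by its cut-offs. If the 90% interval is taken as the rule, the probabilities are 28.8% and 6.6%.

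The same applies to a null of 18%. At 0.20 the cut-off is 7 of 25 (size 14.9%), with power 43.9% at a true ORR of 25% and 65.9% at 30%. With the 90% limit the cut-off is 9 of 25, with power 14.9% and 32.3%.

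**Step 4: is 18% the only defensible null?** The same row of Table JVDF.1 gives 10.7% for PD-L1 below 1%, 16.5% for 1–49% and 45.2% for 50% or more. The pooled rate therefore depends on the PD-L1 mix. Cohort C is not selected on PD-L1 and admits one to three prior lines. The Introduction also cites 14% to 22% for two other PD-1/PD-L1 antibodies in unselected patients across three tumour types including lung. A null of 15% lies inside that range. A null of 10% lies below it and close to the PD-L1-negative figure.

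**The case for a change.** The strongest case for the concern is that a power figure ought to belong to an analysis that will be carried out, and here none does. At each of the six planning cut-offs the 90% interval would still contain the null. The lower limits are 8.2% (5/25, null 10%), 11.0% (6/25, 15%), 6.8% (5/30, 10%), 11.5% (7/30, 15%), 23.6% (10/25, 30%) and 30.5% (12/25, 35%). Disclaiming a decision rule does not say which analysis has the stated power, and ORR will still inform next steps.

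What stands is that the planning level and the interval level differ, and that a reader who silently equates them will expect too much. But 0.20 is printed in the same sentence as the power, the SAP calls it nominal for the previously treated cohorts, and both documents say what the figures are for. A lenient planning level beside a wider descriptive interval is a presentation choice. The interval is the more cautious of the two, so the report would not overstate activity.

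On Cohort C, it stands that 10% and 15% are below 18%, and that exceeding them would not show a contribution from ramucirumab. No choice of null would show that in a single-arm cohort of 25, and the documents do not claim it. Moving the null to 18% would prefer one cited value over others in the same protocol and would alter no planned analysis.

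**Conclusion.** The concern does not hold. The stated 57.9% to 90.2% is exact for the one-sided 0.20 level declared with it. The alternative 27.4% to 65.5% applies only if the 90% lower limit must exceed the null, a requirement that appears in neither document. ORR is a secondary, preliminary endpoint. It is reported by estimation, with no go/no-go threshold and with safety as the basis for cohort size. The Cohort C null is used only in the reference table.

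Restating the table at 0.05, adding an 80% bound or choosing another null would change how the planning reference is presented and nothing in the sample size, the reported estimates or the intervals.

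This rests on two assumptions. The first is that the plan is followed as written, so that no comparison of the interval with a null is introduced later as a success rule. If one were, the last column of the first table would become the relevant power. The second is that all 25 or 30 patients are in the denominator; pooling Phase 1a patients, as SAP 5.3.1 allows, would shift the figures.
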